7. SAFETY ANALYSES

Analysis of safety data will be conducted on the Safety Analysis Set, unless otherwise specified in the following sections. The treatment-emergent (TE) period is defined as the time period from the first dose date of study treatment up to and including last exposure date after permanent discontinuation of study drug.

7.1. Adverse Events and Deaths

7.1.1. Adverse Event Dictionary

Clinical and laboratory AEs will be coded using the current version of MedDRA. System organ class (SOC), high-level group term (HLGT), high-level term (HLT), preferred term (PT), and lower-level term (LLT) will be provided in the AE dataset.

7.1.2. Adverse Event Severity

Adverse events are graded by the investigator as Grade 1, 2, 3, 4, or 5 according to toxicity criteria specified in the protocol. The severity grade of events for which the investigator did not record severity will be categorized as “missing” for tabular summaries and data listings. The missing category will be listed last in summary presentation.

7.1.3. Relationship of Adverse Events to Study Drug

Related AEs are those for which the investigator selected “Related” on the AE eCRF to the question of “Related to Study Treatment.” Relatedness will always default to the investigator’s choice, not that of the medical monitor. Events for which the investigator did not record relationship to study drug will be considered related to study drug for summary purposes. However, by-participant data listings will show the relationship as missing.

7.1.4. Relationship of Adverse Events to Study Procedure

Study procedure related AEs are those for which the investigator selected “Yes” on the AE eCRF to the question of “Related to Study Procedures.” Relatedness will always default to the investigator’s choice, not that of the medical monitor. Events for which the investigator did not record relationships to study procedure will be shown as missing from that captured on the eCRF in by-participant data listings.

7.1.5. Serious Adverse Events

Serious adverse events (SAEs) will be identified and captured as SAEs if the AEs met the definitions of SAEs that were specified in the study protocol. SAEs captured and stored in the clinical database will be reconciled with the SAE database from the Gilead Patient Safety (PS) Department before data finalization.

7.1.6. Treatment-Emergent Adverse Events

7.1.6.1. Definition of Treatment-Emergent Adverse Events

Treatment-emergent adverse events (TEAEs) are defined as:

- Any AEs that start during the TE period.
- Any AEs leading to premature discontinuation of study drug.

7.1.6.2. Incomplete Dates

If the start date of the AE is incomplete and the AE stop date is not prior to the first dosing date of study drug, then the month and year (or year alone if month is not recorded) of start determine whether an AE is TE. The event is considered TE if both of the following 2 criteria are met:

- The AE start date is the same as or after the month and year (or year) of the first dosing date of study drug, and
- The AE start date is the same as or before the month and year (or year) of the last day of the TE period

An AE with completely missing start and stop dates, or with the start date missing and a stop date later than the first dosing date of study drug, will be considered to be TE. In addition, an AE with the start date missing and incomplete stop date with the same or later month and year (or year alone if month is not recorded) as the first dosing date of study drug will be considered TE.

7.1.7. Summaries of Adverse Events and Deaths

TEAEs will be summarized based on the Safety Analysis Set.

A brief, high-level summary of the number and percentage of participants who experienced at least 1 TEAE in the categories described below will be provided. All deaths observed in the study will also be included in this summary.

The number and percentage of participants who experienced at least 1 TEAE will be provided and summarized by SOC, HLT, and PT as follows:

- TEAEs

For the AE categories described below, summaries will be provided by SOC and PT:

- TEAEs by severity
- TEAEs with Grade 3 or higher
- TEAEs with Grade 2 or higher

- TE treatment-related AEs
- TE VES-related AEs
- TE VRC07-523LS-related AEs
- TE CAP256V2LS-related AEs
- TE treatment-related AEs with Grade 3 or higher
- TE treatment-related AEs with Grade 2 or higher
- TE SAEs
- TE treatment-related SAEs
- TEAEs leading to death (i.e., Grade 5 AEs)
- TEAEs leading to premature discontinuation of any study drug
- TEAEs leading to premature discontinuation of study

Multiple events will be counted only once per participant in each summary. Adverse events will be summarized and listed first in alphabetic order of SOC (and HLT within each SOC if applicable), and then by PT in descending order of total frequency within each SOC. For summaries by severity grade, the worst severity will be used for those AEs that occurred more than once in an individual participant during the study.

In addition to the above summary tables, all TEAEs, Grade 3 or Higher TEAEs, TE SAEs, TE treatment-related AEs, Grade 3 or Higher TE treatment-related AEs, Grade 2 or Higher TE treatment-related AEs, and TE treatment-related SAEs will be summarized by PT only, in descending order of total frequency.

In addition, data listings will be provided for the following:

- All AEs, including whether the event is TE
- All SAEs
- All Deaths
- All AEs leading to premature discontinuation of any study drug

7.1.8. Additional Analysis of Adverse Events

The following categories of TEAEs of interest will be summarized:

- Infusion related reactions, as defined per eCRF (i.e., AE with “Yes” answer to “Is this part of an infusion-related reaction?” in AE eCRF). The denominator for the percentage calculation will be based on the number of participants who received at least one infusion in the Safety Analysis Set.
- Potential Cytokine Release Syndrome (CRS) and Flu-like AEs, utilizing a MedDRA search term (MST) list “Cytokine Release Syndrome - HIV Cure therapy” developed by Gilead. The denominator for the percentage calculation will be based on the number of participants in the Safety Analysis Set.

For each AE of interest category, the number and percentage of participants who experienced any of the above events will be summarized by SOC, PT and severity. AEs of each interest category will be summarized by PT only, in descending order of total frequency. The number and percentage of participants who experienced treatment related potentially CRS and flu-like AEs will be summarized by PT and by SOC, PT and severity. In addition, the number and percentage of participants who experienced treatment related potentially CRS and flu-like AEs will be summarized separately by PT for VES-related, VRC07-523LS-related, and CAP256V2LS-related events. Data listings will be provided for each AE of interest category.

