dosing. The latent HIV-1 reservoir was evaluated by Intact Proviral DNA Assay (IPDA) and Inducible Virus Production Assay (IVPA). No consistent change was observed following VES or placebo dosing by IVPA or total HIV DNA measured by IPDA. However, a significant decrease in the estimated frequency of cells harboring intact HIV DNA measured by IPDA was observed in the VES group ($P = 0.046$) but not in the placebo group. The delayed viral rebound was associated with lower intact proviral DNA at the end of VES treatment {[Riddler 2021](#), [SenGupta 2021](#)}.

Pharmacokinetics/Pharmacodynamics Results

Vesatolimod PK following administration of 4 mg or 6 mg was similar to that observed previously (Studies GS-US-243-0101 and GS-US-382-1450). Mean exposure (AUC and C_{max}) following administration of VES 8 mg was numerically higher than previously observed following administration of VES 8 mg or 12 mg (Studies GS-US-243-0101 and GS-US-382-1450); this may be due to the small number of participants in this group (N = 3).

The evaluated PD markers (cytokine, ISG markers, and lymphocyte activation) were induced following dosing with VES in PWH. The cytokine markers with the greatest fold increases in serum following dosing with VES were IP-10 and IFN- α . Overall, absolute levels of IFN- α production were low and comparable to previous studies of VES. There was a 4.11-fold maximal mean increase from baseline in IL-1RA observed 1 day after the 10th VES dose. There was a 6.02-fold maximal mean increase from baseline in IP-10 observed 1 day after the 10th VES dose. There was a 3.45-fold maximal mean increase from baseline in inducible T cell alpha chemoattractant (ITAC) observed 1 day after the 10th dose of VES. There was a 62.57-fold maximal mean increase from baseline in IFN- α observed 1 day after the fourth dose of VES.

All ISGs assessed in this study were induced with the greatest mean inductions of 19.71-fold, 7.44-fold, and 10.29-fold increases for ISG-15, OAS-1, and MX1, respectively. IL-1RA, IP10, and ITAC decreased to baseline levels 7 days after each dosing cycle, while IFN- α decreased to baseline levels by Day 1 of the next VES dose. An increase in the activation of T cells, DCs (CD54+pDC), monocytes (CD14+CD16+), T cells (CD4+HLA-DR+CD38+ and CD8+HLA-DR+CD38+) and NK cells (CD69+CD56+CD16+, CD69+CD56dimCD16- and CD69+CD56brCD16dim) was observed 1 and 3 days following dosing with VES, which returned to baseline 13 days after each dose.

Safety Results

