
Adverse events were reported in 22 of 25 participants (88.0%) as follows: VES 4 mg, 2 of 2 participants (100.0%); VES 4/6 mg, 3 of 4 participants (75.0%); VES 6 mg, 5 of 5 participants (100.0%); VES 6/8 mg, 3 of 3 participants (100.0%); VES 8 mg, 3 of 3 participants (100.0%); and placebo, 6 of 8 participants (75.0%). No deaths, study drug-related SAEs, pregnancies, or AEs leading to discontinuation of study drug were reported. The most common AEs in the VES group (occurring in > 2 participants) were headache and nausea (5 participants each), chills (4 participants), and sinusitis, arthralgia, fatigue, lymphadenopathy, and pyrexia (3 participants each). The most common AEs in the placebo group (occurring in > 1 participant) were headache (3 participants) and sinusitis (2 participants). Nine participants (53%) who received VES and 1 participant (13%) who received placebo experienced study drug-related AEs. The majority of

the VES-related AEs were mild, transient influenza-like symptoms: 2 participants with fatigue, 3 participants with chills, 2 participants with pyrexia, 3 participants with headache, and 3 participants with lymphadenopathy. One participant who received VES had Grade 3 AEs of gout, arthralgia, and sciatica exacerbation occurring on Days 102, 109, and 113, respectively (between Doses 8 and 9), that were considered study drug-related, as well as an unrelated Grade 3 AE of viral gastroenteritis. One participant who received VES had a Grade 2 SAE of chronic gastritis that was not considered related to study drug. There were no Grade 3 or 4 AEs or SAEs reported in the placebo group.

Overall 19 of 25 participants (76.0%) had any graded laboratory abnormality as follows: VES 4 mg, 2 of 2 participants; (100.0%); VES 4/6 mg, 4 of 4 participants (100.0%); VES 6 mg, 4 of 5 participants (80.0%); VES 6/8 mg, 1 of 3 participants (33.3%); VES 8 mg, 2 of 2 participants (100.0%); and placebo, 6 of 8 participants (75.0%). The majority of laboratory abnormalities were Grade 1 or 2 in severity. One participant with a history of diabetes who received VES had transient Grade 3 nonfasting hyperglycemia, and Grade 3 glycosuria. No Grade 4 laboratory abnormalities were observed. There were no treatment-emergent graded abnormalities in platelets or lymphocytes.

Conclusions

This study demonstrated that:

- Multiple doses of VES (up to 8 mg) were well tolerated.

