Cytokine release syndrome	Fever with or without constitutional symptoms	Hypotension responding to fluids; hypoxia responding to $< 40\% O_2$	Hypotension managed with one pressor; hypoxia requiring $\geq 40\% O_2$	Life-threatening consequences; urgent intervention indicated	Death
---------------------------	---	--	---	--	-------

Definition: A disorder characterized by fever, tachypnea, headache, tachycardia, hypotension, rash, and/or hypoxia caused by the release of cytokines.

Navigational Note: Also consider reporting other organ dysfunctions including neurological toxicities such as: Psychiatric disorders: Hallucinations or Confusion; Nervous system disorders: Seizure, Dysphasia, Tremor, or Headache.

CTCAE = Common Terminology Criteria for Adverse Events; IV = intravenous, NSAID = non-steroidal anti-inflammatory drugs

Source: National Cancer Institute Common Terminology Criteria for Adverse Events Version 5.0

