Appendix 4. Adverse Events Category

An adverse event record will be flagged for an AE category for analysis in the raw Adverse Events dataset if its MedDRA PT is included in the pre-specified MST list for the corresponding AE category, under MedDRA Version 28.0.

| AE Category MST Name (Variable Name) | Preferred Terms |
|--|---|
| Cytokine Release Syndrome - HIV Cure therapy | 
• Arthralgia• Capillary leak syndrome• Chills• Fatigue• Headache• Hypotension• Hypoxia• Influenza• Influenza like illness• Malaise• Myalgia• Nausea• Pyrexia• Shock• Tachypnoea• Vomiting• Cytokine storm• Systemic inflammatory response syndrome• Cytokine release syndrome• Haemophagocytic lymphohistiocytosis• Multiple organ dysfunction syndrome• Chronic inflammatory response syndrome• Primary stabbing headache• Immunotoxicity• Immune effector cell-associated HLH-like syndrome |

GS-US-382-5445-Final Analysis-SAP-v1.0

ELECTRONIC SIGNATURES

| Signed by | Meaning of Signature | Server Date (dd-MMM-yyyy hh:mm:ss) |
|------------------|----------------------------------|--|
| PPD | Biostatistics eSigned | 11-Jun-2025 18:45:37 |
| PPD | Clinical Development eSigned | 11-Jun-2025 19:37:28 |
| PPD | Clinical Pharmacology eSigned | 13-Jun-2025 18:42:34 |

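### The SAP's CRS and flu-like category leaves out tachycardia and rash, which the protocol's CRS definition names, and counts listed terms with no link to dosing

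*SAP*

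**What the plan says.** SAP 7.1.8 defines two categories of adverse events of interest. One is infusion-related reactions, identified by an eCRF question. The other is "Potential Cytokine Release Syndrome (CRS) and Flu-like AEs, utilizing a MedDRA search term (MST) list". Under Appendix 4 a record belongs to the category when its preferred term is on the list: "An adverse event record will be flagged for an AE category for analysis in the raw Adverse Events dataset if its MedDRA PT is included". The list begins "Arthralgia• Capillary leak syndrome• Chills• Fatigue• Headache• Hypotension• Hypoxia• Influenza• Influenza like illness• Malaise• Myalgia• Nausea• Pyrexia• Shock• Tachypnoea• Vomiting• Cytokine storm" and continues "Systemic inflammatory response syndrome• Cytokine release syndrome• Haemophagocytic lymphohistiocytosis• Multiple organ dysfunction syndrome• Chronic inflammatory response syndrome• Primary stabbing headache• Immunotoxicity", with one further term for an HLH-like syndrome.

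The counting period comes from SAP section 7: "The treatment-emergent (TE) period is defined as the time period from the first dose date of study treatment up to and including last exposure date". SAP 3.8.1 sets the last exposure date equal to the last study date for anyone who received an antibody infusion, and gives prolonged antibody exposure as the reason.

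Protocol Table 7, used to grade CRS in this trial, defines it as "A disorder characterized by fever, tachypnea, headache, tachycardia, hypotension, rash, and/or hypoxia caused by the release of cytokines".

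SAP 7.1.8 also plans the CRS and flu-like category restricted to treatment-related events, separate tables for events related to VES, VRC07-523LS and CAP256V2LS, and listings. It plans no display by dose number or by time since dosing.

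**The concern.** There are two separate gaps. First, the list does not match the definition the protocol uses: two named features have no term, and neither document says why. Second, nothing ties an event to a dose, so a headache or influenza in month twelve counts the same as one on the evening of Dose 1.

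This matters because CRS is a central risk here. Protocol 1.5 reports a Grade 3 serious CRS event in a healthy volunteer given VES 8 mg with another anti-HIV antibody, and Protocol 7.7.1 accepts that the present regimen may raise the risk. Protocol 1.5 also says VES-related events are more common after Doses 1 and 2. With no control arm, timing relative to dosing is one of the few objective ways to separate a drug effect from background. Protocol 1.5 names symptoms of retroviral syndrome as a risk of the treatment interruption (ATI), so late flu-like events have a competing cause.

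**Working it through.** **Coverage of the definition.** Table 7 features against the Appendix 4 list:

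- fever: listed (Pyrexia)
- tachypnea: listed (Tachypnoea)
- headache: listed
- hypotension: listed
- hypoxia: listed
- tachycardia: no term
- rash: no term

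Coverage is 5 of 7. All seven manifestations named in the Protocol 7.7.1 monitoring plan (fever, fatigue, chills, myalgia, headache, hypoxia, hypotension) are listed, as is the diagnosis Cytokine release syndrome.

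**Length of the counting period.** The last Period 4 visit is Day 413 (Protocol Table 6) and the end-of-study visit is one week later (Protocol 6.8). (413 + 7)/7 = 420/7 = 60.0 weeks, which reproduces the stated maximum of 60 weeks. Days 0 to 420 are 421 days.

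**Share of that period near a dose.** Dosing days are 0, 14, 28, ..., 126 for VES (10 doses) and 7 for the antibodies. Assign each day to the most recent dose:

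- 0–7 days after: Dose 1 contributes Days 0–6 (7 days), the infusion Days 7–13 (7 days), and Doses 2 to 10 contribute 8 days each. 7 + 7 + 9 × 8 = 86 days; 86/421 = 20%.
- 8–13 days after: Doses 2 to 10 contribute 6 days each. 9 × 6 = 54 days; 54/421 = 13%.
- 14 days or more after: 421 − 86 − 54 = 281 days; 281/421 = 67%.
- After the last VES dose: 420 − 126 = 294 days; 294/421 = 70%.

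These are shares of scheduled time, not of events. Postponing the ATI lengthens the schedule and leaving early shortens it.

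**What background alone could do.** The documents give no background rate for the listed terms, so this uses assumed rates. If a participant has probability p per 4 weeks of an unrelated listed event, at a constant rate, the expected number flagged among 25 is 25 × [1 − (1 − p)^(T/28)].

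| Assumed p per 4 weeks | T = 420 days | T = 86 days (0–7 days after a dose) |
|---|---|---|
| 1% | 3.5 | 0.8 |
| 5% | 13.4 | 3.6 |
| 10% | 19.9 | 6.9 |

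**Evidence from the earlier VES study (Protocol 1.2.4.1.2).** The most common placebo events were "headache (3 participants) and sinusitis (2 participants"). Headache was 3/8 = 37.5% on placebo (exact 95% CI 8.5% to 75.5%) and 5/17 = 29.4% on VES (10.3% to 56.0%), so an all-cause headache count did not separate the arms. The groups are small and follow-up differed.

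**What the documents offer for choosing a window.** In the same study IL-1RA, IP-10 and ITAC "decreased to baseline levels 7 days after each dosing cycle". IFN-alpha returned to baseline only by the next dose, and cell activation by 13 days. No single cut-point follows from this.

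**The case against.** The strongest reply is that the category does what its title says. It is meant to be broad, and headache, fatigue, malaise, myalgia and joint pain are the protocol's own examples of influenza-like events. Table 7 lists features joined by and/or, not required criteria. Its Grade 1 is anchored on fever and its Grades 2 and 3 on hypotension and hypoxia, so isolated tachycardia or isolated rash meets none of those. Such an event would still appear in the general tables and listings of SAP 7.1.7, and pulse is among the vital signs summarised by time point under SAP 7.3. All of this stands.

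It is also fair that the treatment-related and per-drug tables reduce over-counting, and that late events in at most 25 participants can be read from listings. That stands in part. Those tables use the same list, rest on open-label investigator attribution, and count a missing relationship as related (SAP 7.1.3). They do not replace timing.

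A reader might infer that 80% of flagged events will be unrelated to dosing, or that an onset window would have removed the placebo headaches. Neither follows. The 80% is calendar time, and the protocol gives no onset dates for those headaches. Nor do the documents establish 0–7 days as the right headline window, since IFN-alpha and cell activation took longer to return to baseline.

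**Conclusion.** The point holds as a modest, inexpensive improvement. Two named features are missing from the list without explanation, and the all-cause table counts listed terms over up to about 60 weeks with no link to dosing.

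A reader might go further and conclude that the category misses the key safety signal. The documents do not support that: diagnosed CRS, fever, hypotension and hypoxia are all captured. What is lost from the category is a participant whose only relevant event is tachycardia or rash. The second effect is dilution. The all-cause count can include background or ATI-related symptoms months after dosing, by an amount that depends on a background rate the documents do not give. The primary endpoints (all treatment-emergent adverse events and graded laboratory abnormalities) are unaffected.

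The day counts assume the full protocol schedule with every dose on its nominal day.

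**What to change.** 1. Add tachycardia terms (Tachycardia, Sinus tachycardia, Heart rate increased) and rash terms to Appendix 4. If the sponsor's list is fixed, add them as a study-specific supplement.
2. Keep the planned any-onset, treatment-related and per-drug tables.
3. Add one table of CRS and flu-like events by time since the most recent VES dose or antibody infusion, for example 0–7 days, 8–13 days, and 14 days or more, and by dose number with the infusion as its own row. Show the preferred term Cytokine release syndrome on its own line. Assign an onset on a dosing day to that day's dose, and give incomplete onset dates a separate row.
4. State that the cut-points are a choice guided by the marker data in Protocol 1.2.4.1.2.

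The cost is SAP wording, derived flags from dates already collected, and one extra table. Rash terms will bring in some unrelated events, which the timing columns will help a reader recognise. Under SAP section 1, changes made after the SAP is final are documented in the clinical study report.

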7.2. Laboratory Evaluations

Laboratory data collected during the study will be analyzed and summarized using both quantitative and qualitative methods. The analysis will be based on values reported in conventional units. When values are below the LOQ, they will be listed as such, and the closest imputed value will be used for the purpose of calculating summary statistics as specified in Section 3.7.

Summaries of laboratory data will be provided for the Safety Analysis Set and will include data collected in TE period defined at the beginning of Section 7. A by-participant listing for laboratory test results will be provided by participant ID number and visit in chronological order for hematology, serum chemistry, and urinalysis separately. Values falling outside of the relevant reference range and/or having a severity grade of 1 or higher will be flagged in the data listings, as appropriate.

No formal statistical testing is planned.

7.2.1. Summaries of Numeric Laboratory Results

Descriptive statistics will be provided for each laboratory test specified in the study protocol as follows, as appropriate:

- Baseline values
- Values at each postbaseline visit
- Change from baseline at each postbaseline visit

A baseline laboratory value will be defined as the last measurement obtained on or prior to the date/time of first dose of study drug. Change from baseline to a postbaseline visit will be defined

as the visit value minus the baseline value. The mean, median, Q1, Q3, minimum, and maximum values will be displayed to the reported number of digits; SD values will be displayed to the reported number of digits plus 1.

In the case of multiple values in an analysis window, data will be selected for analysis as described in Section 3.8.3.

